3.2 General study level definitions

3.2.1 Baseline values

The DV0004 Baseline value is defined as the last non-missing measurement prior to the first self-injection at Visit 1 (Baseline). If a scheduled Baseline assessment is taken on the same day as the first administration of study medication, then the assessment will be assumed to have been performed prior to study medication.

3.2.2 Relative Day

The relative day will be included in different listings and will be calculated as follows:

- If the start (stop) date occurred on or after the first dose in DV0004, but prior to the drug stop date, relative day is calculated as start (stop) date minus first dose date + 1
- If the start (stop) date occurred after the last dose of bimekizumab, the relative day to the most recent dose is calculated as start (stop) date minus most recent dose date. The relative day in this situation should be preceded by a '+'
- If the start (stop) date occurred before the first dose in DV0004, the relative day is calculated as start (stop) date minus first dose date. The relative day in this situation should be preceded by a '-'.

Relative day will only be computed for fully completed dates and will be missing for partial dates.

3.3 Protocol deviations

Important protocol deviations are deviations from the protocol which could potentially have a meaningful impact on the primary objective of the study. The criteria for identifying important protocol deviations and the classification of important protocol deviations will be defined within the project Data Cleaning Plan. To the extent feasible, the rules for identifying protocol deviations will be defined without review of the data and without consideration of the frequency of occurrence of such deviations. Whenever possible, criteria for identifying important protocol deviations will be implemented algorithmically to ensure consistency in the classification of important protocol deviations across all subjects.

Following the declaration of the global COVID-19 pandemic by the World Health Organization in March 2020, protocol deviations will be identified as “related to COVID-19” where applicable.

3.4 Analysis sets

3.4.1 Enrolled Set

The Enrolled Set (ES) will consist of all subjects who have given informed consent for DV0004.

3.4.2 Safety Set

Two different Safety Sets (SS) will be generated (1 for each device presentation): the bimekizumab-SS-1mL Safety Set (SS-s) and the bimekizumab-AI-1mL Safety Set (SS-a). Each SS will consist of all subjects in the study who receive at least 1 dose of bimekizumab by the indicated self-injecting device presentations. Safety variables will be analyzed using the SS-s and SS-a.

3.4.3 Full Analysis Set

Two different Full Analysis Sets (FAS) will be generated (1 for each device presentation): the bimekizumab-SS-1mL Full Analysis Set (FAS-s) and the bimekizumab-AI-1mL Full Analysis Set (FAS-a). Each FAS will consist of all subjects in the SS-s or SS-a who self-inject at least 1 dose of bimekizumab using the given device and who have an assessment of self-injection. All self-injection related endpoints will be analyzed using the FAS-s and FAS-a.

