7.1.2.1 Instruction for use of bimekizumab-AI-1mL

The bimekizumab-AI-1mL is used to administer an sc injection in either the right or left lateral abdominal wall or the right or left outer thigh without massage. Rotation between the injection sites should be observed. Treatment of the injection site with an anesthetic cream prior to dosing is not permitted.

During the study (at Baseline and Week 4), the bimekizumab-AI-1mL devices will be used to administer 160mg injections of bimekizumab. To use the bimekizumab-AI-1mL, the ring-pull cap is removed and the device is depressed on the injection site. The auto-injector provides needle insertion, dose delivery, and needle protection through an extending and locking shroud. Needle protection is performed by a shroud that will deploy should the auto-injector lose contact with the skin during an injection.

Additional instructions for device use, including the injection angle, are provided in the IFU.

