13.4 Termination of the study

UCB reserves the right to temporarily suspend or prematurely discontinue this study either at a single site, multiple sites, or at all sites at any time for reasons including, but not limited to, safety or ethical issues, inaccurate or incomplete data recording, noncompliance, or unsatisfactory enrollment with respect to quality or quantity.

The study may also be temporarily suspended or prematurely terminated in either of the following situations:

- Severe or serious injection site reaction (eg, bleeding, bruising, pain) that, in the opinion of the Investigator, the overseeing IRB, or the Sponsor, is likely to be seen in other enrolled subjects who have not yet been injected with bimekizumab.
- Unexpected device presentation malfunction leading to a failed or incomplete injection, or resulting in an SAE that, in the opinion of the Investigator, the overseeing IRB, or the Sponsor, is likely to be seen in other enrolled subjects who have not yet been injected with bimekizumab.

If the study is prematurely terminated or suspended, UCB (or designee) will inform the Investigators/institutions and the regulatory authority(ies) of the termination or suspension and the reason(s) for the termination or suspension, in accordance with applicable regulatory requirement(s). The IRB/EC should also be informed and provided with reason(s) for the termination or suspension by the Sponsor or by the Investigator/institution, as specified by the applicable regulatory requirement(s). In addition, arrangements will be made for the return of all used or unused IMP and other material in accordance with UCB procedures for the study.

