10 SAFETY ANALYSES

All safety analysis will be performed for SS-s and SS-a.

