10.2.1 Adverse device effects

Adverse events are recorded at the AE CRF page at the time when they occur. If an AE is related to the device by assessment of the investigator it is counted as an ADE.

All ADE data will be listed, and no statistical testing will be performed. Only treatment-emergent ADEs will be included in the summary tables. Treatment-emergent ADEs (TEADEs) will be defined as events related to the study device that have a start date on or following the first self. administration of study treatment in DV0004 through the final self-administration of study treatment + 7 days. The device SFU will occur 1 week after the last self-administration.

All ADEs will be coded and classified by system organ class, high level term, and preferred term. Adverse device effects will be summarized by the frequency and percentage of subjects having 1 or more of the events in question. Additional planned summaries include overall ADEs and SADEs. Summaries to be presented include:

- Incidence of TEADEs – Overview
- Incidence of TEADEs by SOC, HLT, and PT
- Incidence of serious TEADEs by SOC, HLT, and PT
- Incidence of TEADEs leading to death
- Incidence of TEADEs leading to discontinuation
- Incidence of non-TEADEs (only listed and not summarized in a table)

For definition of serious, unanticipated and unanticipated serious ADEs (USADEs) see protocol of DV0004.

Adverse device effects which started before DV0004 Week 4 and were ongoing at the data cut off will be included with the status remaining as ongoing. Adverse device effects which were ongoing at DV0004 Week 4 but with an end date before the data cut off will be included with their end date as recorded.

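### Analysis-set entry requires a dose by the device, so a subject whose only attempt delivers nothing is missing from the Baseline success percentage and from the device-integrity and ADE summary tables

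*SAP*

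**What the plan says.** SAP 3.4.2 admits to each Safety Set "all subjects in the study who receive at least 1 dose of bimekizumab by the indicated self-injecting device presentations". SAP 3.4.3 then takes, from within that set, the subjects "who self-inject at least 1 dose of bimekizumab using the given device and who have an assessment of self-injection". Protocol 14.1 has the same two rules. Neither document admits a subject on an attempt, and neither says whether a dose means a complete, partial or merely attempted one.

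The sets are used as follows:

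- **Success and device integrity.** SAP 3.4.3 states: "All self-injection related endpoints will be analyzed using the FAS-s and FAS-a". SAP 11 and 11.3 put the structural and functional integrity tables on the same sets.
- **Safety.** SAP 10 states: "All safety analysis will be performed for SS-s and SS-a". SAP 10.2.1 adds: "Only treatment-emergent ADEs will be included in the summary tables". The treatment-emergent window opens at the first self-administration in DV0004.
- **Success definition.** Under SAP 11.1 and 11.2 the first limb is that the whole dose was delivered and the container is empty. The second limb concerns device-related events.

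The protocol foresees that an attempt may fail. Section 13.4 lists, among reasons to suspend or stop the study, "Unexpected device presentation malfunction leading to a failed or incomplete injection". Section 7.1.2.1 says of the auto-injector: "Needle protection is performed by a shroud that will deploy should the auto-injector lose contact with the skin during an injection". Section 6.3 lets a subject leave DV0004 and continue in PA0012.

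**The concern.** A randomised, trained subject who tries at Baseline and delivers nothing is the plainest failure of the secondary objective, which is the ability to self-inject immediately after training. If that subject then leaves the substudy, no dose was received by the device, so the subject is outside both sets. The failure is removed before anything is counted.

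The rule also treats like cases differently. Two subjects can have the same Baseline failure. The one who later receives a dose by the device enters the FAS, and the Baseline failure counts. The one who never does is dropped.

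The same gap reaches safety. Protocol 11.1.1.1 defines ADEs as events arising from device malfunction, inadequate instructions or use error. A non-delivering attempt could produce such an event, and in a never-dosed subject it would be absent from the summary tables. With no hypothesis test planned, the estimate and its interval are the whole result, so the denominator matters.

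**Working it through.** **Inputs from the documents.** About 200 subjects at 1:1 (SAP 2.3.2, 2.3.6), so 200/2 = 100 per arm, which agrees with the plan's own figure. 90% exact binomial intervals (SAP 3.1, 11.1), taken here as two-sided Clopper-Pearson with 5% in each tail.

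**Assumed input.** k = number of subjects per arm whose only attempt delivers nothing and who never receive a dose by the device. The documents give no value; I use 1 to 5 of 100 attempts.

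**Step 1: follow this subject through the rules.**

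| Output | Set or rule | Subject counted? |
|---|---|---|
| Baseline success (SAP 11.2) | FAS | No |
| Baseline integrity tables (SAP 11.3.4, 11.3.5) | FAS | No |
| TEADE tables (SAP 10.2.1) | Safety Set, from first self-administration | No |
| Week 4 success (SAP 11.1) | FAS, observed data only (SAP 3.1) | No, under any FAS rule: no Week 4 observation |
| Disposition, discontinuation reasons, exclusion listing (SAP 5.1) | Enrolled Set | Yes |

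**Step 2: size at Baseline, all other subjects succeeding.** As written the percentage is (100 − k)/(100 − k) = 100%, with lower limit 0.05^(1/(100 − k)). Counting the failures gives (100 − k)/100, so the difference is k percentage points.

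| k | As written (90% CI) | Failures counted (90% CI) |
|---|---|---|
| 1 | 99/99 = 100% (97.0–100) | 99/100 = 99.0% (95.3–99.9) |
| 2 | 98/98 = 100% (97.0–100) | 98/100 = 98.0% (93.8–99.6) |
| 3 | 97/97 = 100% (97.0–100) | 97/100 = 97.0% (92.4–99.2) |
| 5 | 95/95 = 100% (96.9–100) | 95/100 = 95.0% (89.8–98.0) |

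**Step 3: the same with 2 further failures among dosed subjects.** k = 2: 96/98 = 98.0% (93.7–99.6) as written, against 96/100 = 96.0% (91.1–98.6). k = 5: 93/95 = 97.9% (93.5–99.6) against 93/100 = 93.0% (87.3–96.7).

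**Step 4: ADE tables, if each such subject had an ADE and nobody else did.** k = 1: 0/99 as written against 1/100 = 1.0%. k = 2: 0/98 against 2/100 = 2.0%.

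**Step 5: who is not affected.** A subject dosed at Baseline whose Week 4 attempt fails is already in both sets, and the Week 4 failure counts.

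**The case against.** The strongest reply is that the gap is narrow. It needs zero delivery, no later dose by the device, and exit from the substudy, all in one subject. The cited examples do not establish zero delivery. The shroud wording concerns loss of contact while an injection is under way, which fits partial delivery at least as well, and Protocol 13.4 is a termination criterion that gives no rate. An incomplete delivery can be scored as a failure within the FAS if a partial dose counts as a dose. The study is descriptive, with no success threshold, so a shift of one or two points in a secondary percentage changes no decision rule. All of this stands, and it limits the size of the point.

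Three stronger readings might be inferred, and the documents do not support them:

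- **That the primary percentage is biased by this rule.** SAP 3.1 bases outcome percentages on observed data, so this subject is outside the Week 4 denominator whatever the FAS rule says.
- **That a failure is counted only if the subject later succeeds.** Entry needs a later dose and an assessment, not a successful injection.
- **That ADEs from malfunction or use error are lost as a class.** Only events in never-dosed subjects are at issue. SAP 4.2 treats events of uncertain timing as treatment-emergent. SAP 10.2.1 has all ADEs listed, although SAP 10 ties safety analysis to the Safety Set. Protocol 11.1.2.2 requires device deficiencies to be reported even for unused devices.

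The subjects are therefore not invisible, since the Enrolled Set outputs in SAP 5.1 show them. But a listing does not correct a percentage. Nor does item 3 of SAP 3.8 help: it keeps subjects with important deviations in the FAS but does not waive the dose condition.

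**Conclusion.** The point holds for the Baseline success percentage, the Baseline device-integrity tables and the TEADE summary tables, and only for subjects who never receive a dose by the device. For them the analysis sets are selected on part of the outcome. This is a stated rule rather than a missing detail, and it can only favour the device.

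With 100 attempts per arm and all others succeeding, each such subject is worth one percentage point. One of them lowers the lower 90% limit from 97.0% to 95.3%, and two lower it to 93.8%. The number of such subjects is an assumption and may be zero, in which case nothing changes. The conclusion rests on the literal reading that zero delivery is not a dose. Partial delivery is undefined and could be handled either way, which also needs settling.

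**What to change.** Amend the SAP as follows and list the changes in SAP 3.8:

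1. Define SS-s and SS-a by at least one attempted self-injection with the given device, whether or not drug was delivered. Define FAS-s and FAS-a in the same way, with an assessment of the attempt.
2. State that an attempt with no delivery or incomplete delivery counts as not safe and effective at that visit.
3. Start the TEADE window at the first attempted self-injection.
4. SAP 11.1 to 11.3 remove assessments where someone other than the subject performed the injection. State that this does not apply when the subject attempted and failed, including when staff then inject. Without this, the same attempts could be removed again after the sets are widened.

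The cost is SAP wording and possibly a slightly less favourable Baseline percentage. The sponsor must also check that the self-injection CRF page identifies attempts with no delivery. SAP 11.1 cites only two of its questions, so the documents do not confirm that it does.

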3.4.4 Pharmacokinetic Per Protocol Set

Two different Pharmacokinetic Per Protocol Sets (PK-PPS) will be generated (1 for each device presentation): the bimekizumab-SS-1mL PK-PPS (PK-PPS-s) and the bimekizumab-AI-1mL PK-PPS (PK-PPS-a). Each PK-PPS will consist of all subjects who receive the same bimekizumab administration (frequency and dose) in the PA0012 feeder studies as in the DV0004 substudy and who have at least 1 evaluable PK assessment in the DV0004 substudy without important protocol deviations that would affect the concentration. Pharmacokinetic variables will be analyzed using the PK-PPS-s and PK-PPS-a.

All PK assessments after baseline assessments from the feeder study will be considered for the one evaluable PK assessment.

3.5 Treatment assignment, treatment and device groups

This is an open-label study and as such all subjects will be summarized according to the treatment that was assigned. The treatment group will be allocated in PA0012 and the device group will be allocated in DV0004.

PA0012 treatment groups

This refers to the study treatment assigned to the subject at the beginning of PA0012 and does not account for the treatment received in the relevant Feeder Study.

All subjects will receive bimekizumab 160mg Q4W sc.

DV0004 device groups

This refers to the study device assigned to the subject at the beginning of DV0004. The DV0004 device groups are as follows:

- Bimekizumab-SS-1mL
- Bimekizumab-AI-1mL.

The outcome variables will be summarized by assigned DV0004 device group. The different DV0004 device groups are reflected in the use of the corresponding analysis set SS-s, SS-a, FAS-s, FAS-a, PK-PPS-s and PK-PPS-a.

3.6 Center pooling strategy

No pooling of centers is planned for this study.

3.7 Coding dictionaries

All ADEs will be coded and classified by system organ class (SOC), high level term (HLT), and preferred term (PT) according version 19.0 of the Medical Dictionary for Regulatory Activities (MedDRA®).

All medications other than the study drug will be classified by World Health Organization (WHO) Anatomical Therapeutic Chemical (ATC) classification, presenting Anatomical Main Group (ATC Level 1), Pharmacological Subgroup (ATC Level 3), and preferred term (PT), using version SEP/2015 of the World Health Organization Drug Dictionary (WHO-DD), according to UCB standard operating procedures (SOP).

Previous and ongoing medical history will be classified by version 19.0 of MedDRA® SOC and PT.

3.8 Changes to protocol-defined analyses

1. Study duration per subject in the protocol is specified as 5 weeks. In this document it is defined as 4 weeks. This accounts for 4 weeks of treatment. The additional week of Safety Follow-Up is still included in the allocation of adverse device events, which includes events occurring up to last dose + 7 days.
2. The analysis sets to be used for the PK data have been amended from the PK Analysis set to the PK Per Protocol Analysis set (PK-PPS) throughout which will allow the exclusion of subjects with important protocol deviations related to PK from the primary analysis.
3. Subjects who had important protocol deviations affecting the primary outcome variable, as confirmed during ongoing data cleaning meetings prior to database lock, will not be excluded from the FAS-s or FAS-a.
4. The pharmacokinetic assessment of anti-bimekizumab antibody status will be measured before self-injection at DV0004 Baseline, and after self-injection at DV0004 Baseline and DV0004 Week 4 (the assessment is taken at Week 4 and Week 8 visits). This is different from the protocol, which incorrectly stated the following:

- Blood samples will be taken before self-injection at the Baseline Visit (PK trough and anti-bimekizumab antibody analysis), Visit 2 Week 4 (PK trough analysis only) and Week 8 of PA0012 (PK trough and anti-bimekizumab antibody analysis).

This text has been updated to the following as presented in Section 9.1:

- [...] blood samples will be taken before self-injection using the assigned self-injecting device presentation at the DV0004 Baseline Visit and DV0004 Week 4 (Visit 2), and before injection by site personnel at PA0012 Week 8 (Visit 3 of PA0012).

3.8.1 Changes related to COVID-19

The impact of the COVID-19 pandemic on study procedures and/or conduct and on the primary safety endpoints (TEADEs, serious TEADEs, and study withdrawal due to TEADEs) will be investigated and additional outputs provided as appropriate. These analyses were not planned as part of the protocol as the pandemic scale was unprecedented.

The additional analyses are described in the following sections of the SAP:

- Subject disposition, including details of impacted visits and effects on collection and reporting of efficacy data (Section 5.1.1)
- Protocol deviations potentially related to COVID-19 (Section 5.2)
- Impact of COVID-19 on study (Section 5.3)
- Demographics, baseline characteristics (Sections 6.1 and 6.2)
- Adverse events (Section 10.2.2)
- Primary outcome variable (Section 11.1)

4 STATISTICAL/ANALYTICAL ISSUES

4.1 Adjustments for covariates

Not applicable.

4.2 Handling of dropouts or missing data

For analyses of ADEs and concomitant medication usage, a complete date must be established in order to correctly identify the ADE or medication as occurring during treatment or not. For purposes of imputing missing components of partially-reported start and stop dates for ADEs and for medication use, the algorithms listed below will be followed. Start and stop dates of ADEs or concomitant medication will be displayed as reported in the subject data listings (i.e., no imputed values will be displayed in data listings).

Partial ADE and concomitant medication start dates will be imputed as follows:

Imputation of Partial Start Dates

- If only the month and year are specified and the month and year of first dose is not the same as the month and year of the start date, then use the 1st of the month
- If only the month and year are specified and the month and year of first dose is the same as the month and year of the start date, then use the date of first dose

- If only the year is specified, and the year of first dose is not the same as the year of the start date, then use the 1st of January of the year of the start date
- If only the year is specified, and the year of first dose is the same as the year of the start date, then use the date of first dose
- If the start date is completely unknown and the stop date is unknown or not prior to the date of first dose, then use the date of first dose.

Imputation of Partial Stop Dates

- If only the month and year are specified, then use the last day of the month
- If only the year is specified, then use December 31st of that year
- If the stop date is completely unknown, do not impute the stop date.

If the imputed stop date is prior to the imputed start date:

- For missing start day and start month:
 - If the year of start date is the same as the year of first dose and the imputed stop date is on or after the date of first dose, then set the start date to the date of first dose
 - Otherwise set to the 1st January of the year of the start date
- For missing start day only
 - If the month and year of the start date is the same as the month and year of first dose and the imputed stop date is on or after the date of first dose, then set the start date to the date of first dose
 - If the month and year of the start date is the same as the month and year of first dose and the imputed stop date is before the date of first dose, then set the start date to the 1st of that month

In the event of ambiguity or incomplete data which makes it impossible to determine whether a medication was concomitant, or an adverse event was treatment emergent, the medication will be considered as concomitant or the adverse event will be considered treatment emergent.

If the intensity of an ADE is unknown, it will be considered as severe. If the relationship to study drug is missing, it is considered as related.

There will be no special procedures for handling missing data for any other data points.

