11.1.2.1 Reporting of adverse device effects

All ADEs and SADEs will be captured on the eCRF. The eCRF will allow Investigators to specify whether an AE or SAE is device-related and will clarify which device presentation is associated with the ADE or SADE.

An Investigator Adverse Device Effect and Device Deficiency form will be provided to the Investigator. The Investigator Adverse Device Effect and Device Deficiency form must be completed in English.

The Investigator (or designee) shall report all SADEs and device deficiencies that might have led to an SAE (if suitable action had not been taken, if intervention had not been made, or if circumstances had been less fortunate) to UCB within 24 hours after knowledge of the event using the appropriate forms in the electronic data capture system. When required by national or local regulations, the Investigator shall also notify the IRB/IEC and regulatory agencies of all reportable events according to national regulations in acceptable timely conditions, and may also be requested by the IRBs to provide annual reports.

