10.2 Adverse events

All AEs (including serious adverse events [SAEs]) will be reported in a common database for PA0012 and DV0004, but only adverse device effects (ADEs), serious adverse device effects (SADEs), and device deficiencies will be summarized in the DV0004 substudy. Specifically, only those AEs related to the use of the investigational medical devices bimekizumab-SS-1mL or bimekizumab-AI-1mL (based on the Investigator's judgement) will be assessed. All AEs (including SAEs) which are not assessed to be related to the investigational devices will be summarized separately in the report for the main PA0012 study. An exception are AEs that are indicated as injection site reactions during self-injection. These will be listed in DV0004 as well as in PA0012.

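### The worst-case rule for missing causality in SAP 4.2 is written for the drug, but ADE status in DV0004 rests on relationship to the device, so a missing device relationship has no stated rule and by default falls out of the ADE summaries

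*SAP*

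**What the plan says.** SAP 4.2 ends with two worst-case rules for event attributes. Unknown ADE intensity is taken as severe, and for causality: "If the relationship to study drug is missing, it is considered as related". It then closes the subject: "There will be no special procedures for handling missing data for any other data points".

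The sections that decide what counts in DV0004 use a different relationship:

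- SAP 10.2.1: "If an AE is related to the device by assessment of the investigator it is counted as an ADE". The definition of a treatment-emergent ADE (TEADE) in the same section also requires relationship to the study device, with onset from the first self-administration to 7 days after the last.
- SAP 10.2: "Specifically, only those AEs related to the use of the investigational medical devices bimekizumab-SS-1mL or bimekizumab-AI-1mL (based on the Investigator's judgement) will be assessed". Other events, those "which are not assessed to be related to the investigational devices will be summarized separately in the report for the main PA0012 study", leave the DV0004 summaries.
- Protocol 11.1.2.1: "The eCRF will allow Investigators to specify whether an AE or SAE is device-related". Device relationship is thus an attribute recorded on the eCRF.

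The protocol keeps the two terms apart. Section 7 defines the IMP as the drug product and defines the device presentation separately. Section 7.2 sends IMP-related events to PA0012, and ADEs and device deficiencies to DV0004.

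**The concern.** The only stated rule for missing causality acts on a field that does not decide whether an event is an ADE. The field that does decide it has no rule. A programmer following the text would find that an event with a blank device relationship fails the ADE criterion, and would drop it from the tables.

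The neighbouring rules in SAP 4.2 all lean the other way: unknown intensity becomes severe, and an event of uncertain timing becomes treatment-emergent. Missing device causality alone would be resolved in favour of the device.

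Occurrence of ADEs is the DV0004 safety variable (SAP 2.2.1.3.4), and SAP 3.8.1 calls TEADEs, serious TEADEs and withdrawals due to TEADEs the primary safety endpoints. If ADEs are rare, one blank field can decide whether an arm reports none or one.

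**Working it through.** The plan gives no figure to reproduce, so the main check is a reading of the rules in order, for an adverse event with onset in the TEADE window and a blank device relationship.

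1. **Does the causality rule in SAP 4.2 apply?** It names the study drug. Protocol 7 and 7.2 separate drug from device, so on its wording it does not.
2. **Does the rule for ambiguous data in SAP 4.2 apply?** It covers whether a medication was concomitant and whether an event was treatment-emergent. It does not cover causality.
3. **Does any other rule for missing data apply?** The closing sentence of SAP 4.2 rules out special procedures for everything else.
4. **Is the event an ADE under SAP 10.2.1?** That needs an investigator assessment that it is device-related. A blank does not supply one.
5. **Where does it go?** Under SAP 10.2, events not assessed as device-related are summarised in the PA0012 report.

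The event is therefore absent from the DV0004 TEADE, serious TEADE and discontinuation tables, and from the COVID-19 breakdowns of them in SAP 10.2.2. If it is an injection site reaction, it is still listed under SAP 10.2 and 10.2.3, but that listing does not put it in the TEADE tables.

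**Does it reach the primary outcome?** SAP 11.1 takes all primary data from the Week 4 self-injection CRF page. Success needs a yes on complete dose and an explicit no on device-related events. The device-relationship item on the AE page is not used, and a blank answer on the self-injection page cannot count as a success. So it does not.

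**Illustration of size.** Inputs:

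- n = 100 per arm (SAP 2.3.6, approximate), assumed to be the denominator.
- The 90% exact binomial method (SAP 3.1). SAP 10.2.1 itself promises only frequencies and percentages for ADEs, so the interval serves here to show precision.
- x = number of subjects with at least one ADE. The number of blanks is not in the documents, so x is varied.

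Incidence is x/n, so one more subject adds 1/100 = 1.0 percentage point. The Clopper-Pearson limits are the 0.05 quantile of Beta(x, n − x + 1) and the 0.95 quantile of Beta(x + 1, n − x). At x = 0 the lower limit is 0 and the upper limit is 1 − 0.05^(1/100) = 2.95%.

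| Subjects with an ADE | Incidence | Exact 90% CI |
|---|---|---|
| 0/100 | 0% | 0 to 2.95% |
| 1/100 | 1% | 0.05 to 4.66% |
| 2/100 | 2% | 0.36 to 6.16% |
| 3/100 | 3% | 0.82 to 7.57% |
| 5/100 | 5% | 1.99 to 10.23% |

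Dropping the only affected subject in an arm would turn 1% (upper limit 4.66%) into 0% (upper limit 2.95%). The table counts subjects, as SAP 10.2.1 does. A blank on a further event in a subject who already has an ADE leaves overall incidence unchanged.

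**The case against.** The strongest reply is that the drug wording is loose. The sentence follows directly on one about ADE intensity, in a section about ADEs and medications, and the device presentations are drug and device in one integral unit (Protocol 2 and 7). On that reading the rule already covers the device. This is possible, but the documents separate the two terms wherever causality is assigned. Even on that reading, SAP 4.2 does not say that the rule applies to the wider pool of adverse events before ADE status is set, which is the only stage at which it could add an event. Two programmers could still reach different counts.

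A second reply is that blanks should be rare. There is a separate form for ADEs and device deficiencies, a prompt to the subject at each visit, 24-hour reporting and reconciliation of serious ADEs, and data-cleaning checks (Protocol 11.1.2, 11.5 and 13.3.2). The eCRF may also force an answer; the documents do not say. This stands as a limit on the likely number. None of it is an analysis rule for a value that stays missing.

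A third reply is that imputing related overrides the investigator's judgement, on which SAP 10.2 rests, and may count events that do not meet the ADE criteria in Protocol 11.1.1.1. This is fair. It is the reason to query first and to keep the count without imputation visible.

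The study is also descriptive and unpowered, and the events remain in the common database and the PA0012 report. That lowers the stakes without supplying the missing rule.

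**Conclusion.** The causality rule in SAP 4.2 is attached to the wrong relationship for ADE classification in DV0004. As written, a device relationship that stays missing removes the event from the ADE summaries by default, contrary to the conservative intent of the section. The exclusion is an inference from SAP 4.2, 10.2 and 10.2.1 together, and it assumes that the drug wording is meant literally.

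The size is unknown and may be zero. With about 100 subjects per arm, each affected subject with no other ADE is worth about 1 percentage point, and the direction always favours the device.

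Two stronger readings are tempting and not supported. A reader might infer that the primary success rate is inflated; the separate CRF question in SAP 11.1, with its explicit no, rules that out by this route. A reader might also infer that drug relationship appears in no DV0004 output. The documents show only that it does not define an ADE: SAP 3.1 promises listings of all documented data, and the contents of the TEADE overview table are not specified.

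This is a small but real error in a stated rule, worth correcting because correction costs so little.

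**What to change.** In SAP 4.2, state that if the relationship to the investigational device is still missing after query, for an adverse event with onset in the TEADE window, the event is considered device-related for the ADE and TEADE summaries. Flag these events in the listing and report how many there are, so that the count based on investigator-assessed events alone can also be read off. Relationship to the drug can be left to PA0012.

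The cost is one sentence, one derivation line and a flag. The downside is that a few events with no real device link may be counted as ADEs; the flag and the reported number keep that visible.
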